10.3.6. Variables for subgroup analysis

Subgroups	ICD10 code	Standard disease code	Note
Hypertension			Refer to 10.3.1
Liver dysfunction			Refer to 10.3.1
Renal impairment			Refer to 10.3.1
	A162		Include only tubercular hemoptysis
	A165		Include only tubercular hemothorax
	B303		
	D500		
	D62		
	D66		Include only hemophiliac bleeding
	D683		Include only hemorrhagic disorder due to circulating anticoagulants
	D698		
	D699		
	E078		Include only tyroid bleeding
	E274		Include only adrenal bleeding
	G361		
Bleeding history	G951		Include only hematomyelia, spinal subdural hemorrhage, hematorrhachis, spinal epidural hemorrhage and spontaneous Cervical Epidural Hematoma
	G968		Include only spinal subarachnoid hemorrhage
	H052		Include only orbital fat hemorrhage
	H113		
	H168		Include only Hemorrhagic keratitis
	H208		Include only hemorrhagic iritis
	H210		
	H313		
	H350		Include only hemorrhagic retinitis and juvenile recurrent
			vitreoretinal hemorrhage
	H356		
	H357		Include only hemorrhagic retinal pigment epithelial detachment
	H405		Include only hemorrhagic glaucoma
	H431		

Subgroups	ICD10 code	Standard disease code	Note
	H448		Include only intraocular hemorrhage
	H470		Include only optic disc hemorrhage and optic nerve sheath hemorrhage
	H603		Include only otitis externa hemorrhagica
	H669		Include only hemorrhagic otitis media
	H738		Include only eardrum bleeding
	H922		
	I213		Include only Atrial thrombus as current complication following acute myocardial infarction
	I230		
	I312		
	I600		
	I601		
	I602		
	I603		
	I604		
	I605		
	I606		
	I607		
	I608		
	I609		
	I610		
	I611		
	I613		
	I614		
	I615		
	I616		
	I618 I619		
	1619 1620		
	1620 1621		
	I629		
	1629 1638		Inculde only hemorrhagic cerebral infarction
	1690		
	I691		
	1780		
	1788		
	1850		
	I864		Include only gastric variceal bleeding
	J041		Include only hemorrhagic tracheitis
	J339		Include only bleeding polyp
	J90		Include only hemorrhagic pleural effusion
	J942		
	J950		Include only bleeding from a tracheostomy site
	K049		Include only hemorrhage in the pulp
	K068		Include only gingival hemorrhage
	K121		Include only hemorrhagic stomatitis
	K137		Include only oral hemorrhage

Subgroups	ICD10 code	Standard disease code	Note
	K148		Include only tongue root submucosal bleeding
	K226		
	K228		Include only esophageal hemorrhage
	K250		
	K252		
	K254		
	K256		
	K260		Exclude acute gastroduodenal mucosal lesion
	K262		
	K264		
	K266		
	K284		
	K290		
	K571		Include only Duodenal diverticulum bleeding
	K573		Include only bleeding from Sigmoid diverticulum, Transverse
			colon diverticulum, Descending colon diverticulum,
			Ascending colon diverticulum and Large intestine
			diverticulum
	K625		
	K649		Include only Hemorrhoidal external hemorrhoids,
			Hemorrhoids and Hemorrhoidal internal hemorrhoids
	K661		
	K762		
	K768		Include only hepatorrhagia
	K859		Include only acute hemorrhagic necrotizing pancreatitis
	K920		
	K921		
	K922		
	L508		Include only hemorrhagic urticaria
	M2506		
	M2509		
	N029		
	N288		Include only perirenal bleeding, nephrorrhagia and idiopathic hematuria
	N300		Include only acute hemorrhagic cystitis
	N304		Include only radiation-induced hemorrhagic cystitis
	N309		Include only hemorrhagic cystitis
	N328		Include only bladder hemorrhage
	N368		Include only urethremorrhagia
	N421		, , , , , , , , , , , , , , , , , , , ,
	N488		Include only penile hemorrhage
	N501		Include only Scrotal hemorrhage and Spermatic cord
			hematoma
	N645		Include only thelorrhagia
	N830		Include only follicular hemorrhage and hemorrhagic follicular
	*		cyst
	N831		Exclude luteal cyst
	N836		*

N837	
N838 Include only ovarian hemorrhage	
N898 Include only vaginal hematoma	
N908 Include only vulval hemorrhage	
N921	
N922	
N923	
N924	
N930	
N938	
N939	
_N950	
0717	
0901	
0902	
R040	
R041	
R042	
_R048	
R049	
R18 Include only hemorrhagic ascites	
R195 Include only fecal occult blood	
R233	
R31	
R571 Include only hemorrhagic shock	
R58	
S000 Include only ecchymoma, hematoma and hemorr	hage
S001 Include only hematoma and hemorrhage	
S002 Include only hematoma	
S003 Include only hematoma and hemorrhage	
S004 Include only hematoma and hemorrhage	
S005 Include only hematoma and hemorrhage	
S007 Include only hematoma and hemorrhage	
S008 Include only hematoma	
S013 Include only hemorrhage	
S050 Include only Corneal hematoma	
S051 Include only traumatic vitreous hemorrhage and t	raumatic
hyphema	
S063 Include only hematoma and hemorrhage	
S064	
S065	
S066	
S068 Include only hematoma, hemorrhage	
S098 Include only hemorrhage	
S100 Include only hematoma	
S101	
S141 Include only hematoma	
S241 Include only hematoma	

Subgroups	ICD10 code	Standard disease code	Note
	S271		
	S272		
	S278		Include only hematoma
	S279		Include only hematoma
	S301		Include only hematoma
	S302		Include only hematoma
	S341		Include only hematoma
	S361		Include only hematoma
	S368		Include only hemorrhage
	S369		Include only hematoma
	S370		Include only hematoma
	S378		Include only hemorrhage
	S390		Include only hematoma
	S400		Include only hematoma
	S408		Include only hematoma
	S500		Include only hematoma
	S501		Include only hematoma
	S600		Include only hematoma
	S601		Include only hematoma
	S701		Include only hematoma
	S800		Include only hematoma
	S801		Include only hematoma
	S902		Include only hematoma
	T009		Include only hematoma and hemorrage
	T060		Include only spinal subarachnoid hemorrhage
	T090		Including only hematoma
	T093		Including only hematoma
	T140		Including only hematoma
	T144		Include only traumatic hematomyelia
	T145		Include only traumatic arterial hematoma
	T146		Include only Intramuscular hematoma
	T794		Include only traumatic hemorrhagic shock
	T810		Include only hematoma and hemorrage
	T811		Include only hemorragic shock
	T876		Include only hematoma
	T905		Include only sequelae after
Hemorrhage stroke			Refer to 10.3.1
-	E244		
	E52		Include only Alcoholic pellagra
	F100		
	G312		
A 1 1 - 1 - 1	G405		Include only alcoholic epilepsy
Alcohol abuse	G621		
	G701		Include only alcoholic neuropathy
	G721		
	H470		Include only alcoholic optic neuropathy
	I426		· • • •

Subgroups	ICD10 code	Standard disease code	Note
	K292		
	K70		
	K852		
	K860		
	T519		
Antiplatelet drug			Refer to 5.4
NSAIDs			Refer to 5.4
	F54		Include only psychogenic gastric ulcer
	K221		
	K227		Include only Barrett's esophagus
	K25		
Dantianlan	K26		
Peptic ulcer	K27		
	K28		
	K51		
	K626		
	K633		
Active cancer			Refer to 10.3.1
Diabetes mellitus			Refer to 10.3.1
Polypharmacy	Polypharmacy		Refer to 5.4

Page 56 of 56

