First, all patients with NVAF who are newly diagnosed and initiated apixaban or warfarin will be extracted from the database. Among these patients, patients with at least one predetermined high bleeding risks will be extracted. In this study, predetermined high bleeding risks are 1) patients with hypertension diagnosis, 2) patients with liver dysfunction, 3) patients with renal dysfunction diagnosis, 4) patients with a history of bleeding, 5) patients with hemorrhagic stroke, 6) patients with alcohol abuse, 7) patients with concomitant used of antiplatelet drugs, 8) patients with chronic (continuously for longer than 90 days) concomitant use of Non-steroidal antiinflammatory drug (NSAID), 9) highly elderly (> 80 years old), 10) patients with refractory hypertension, 11) patients with a history of peptic ulcer diagnosis, 12) patients with active cancer, 13) patients with diabetes mellitus, 14) patients whose body weight is <40kg, 15) patients with polypharmacy (sea Section 5.4 for the definition). Patients with at least one predetermined high bleeding risk factor will be divided into two cohorts, apixaban and warfarin cohorts, based on the first prescribed drug just after the NVAF diagnosis. Patient characteristics will be balanced by using an inverse probability of treatment weighting (IPTW) method to create balanced apixaban and balanced warfarin cohorts. Comparisons will be conducted by using these balanced warfarin and apixaban cohorts (Kaplan-meier curves, incidence rates per 1,000 person-year and hazard ratio with 95% confident intervals). The primary safety and effectiveness analyses are comparison of apixaban with warfarin in patients with at least one predetermined risk factor for bleeding.

- Second, after the first analysis, we will conduct separate interaction analysis of the treatment (apixaban vs. warfarin) and one of the 15 risk factors (e.g., hypertension yes vs no, etc) to see if treatment effects are consistent among patients with or without each specific factor
- Third, patients will be stratified by risk factors into 15 subgroups, and same IPTW analyses as described in the step 1 will be conducted only in the subgroups with adequate sample sizes.

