2.2.4. Objectives of other exploratory analysis are

To explore the risk of major bleeding and stroke/SE in the specific populations at higher bleeding risk(s).

As shown above (see 2.1), after interaction analyses of the treatment and risk factors, patients will be stratified to subgroups by each of above mentioned 15 predetermined risk factors separately. Subgroups with adequate sample size will be selected for IPTW analyses.

In the previous feasibility analysis, we found that the numbers of patients with hemorrhagic stroke, alcohol abuse, chronic concomitant used of NSAIDs (for continuously > 90 days), and refractory hypertension were less than 2,000. Due to the insufficient statistical power, these subgroups could be eliminated from the further subgroup analysis. Again, the final decision will be based on the formal evaluation of the number of sample sizes N in those subgroups.

Candidates of exploratory subgroups listed based on the preliminary feasibility analysis

- Exploratory analysis regarding hypertension
- *Exploratory analysis regarding liver dysfunction.*
- Exploratory analysis regarding renal impairment.
- *Exploratory analysis regarding bleeding including intracranial hemorrhage*
- Exploratory analysis regarding concomitant use of antiplatelet drug
- *Exploratory analysis by age*
 - \checkmark > 80 y
 - \checkmark >90 y
- Exploratory analysis regarding peptic ulcer
- Exploratory analysis regarding active cancer
- *Exploratory analysis regarding low body weight (<40kg)*
- Exploratory analysis regarding diabetes mellitus
- *Exploratory analysis regarding polypharmacy (≥6 medicines)*

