Myocardial infarction	1200	Exclude intermediate angina syndrome, preinfarction syndrome, initial arbeits angina, intermediate coronary syndrome
	I210	
	I211	
	I212	
	I214	

Variable Used	ICD-10 Code*	Additional rules
in Study	I240	on Data Extraction
	I241	Exclude Dressler syndrome
Renal impairment	I120	
	I120 I129	
	I129 I139	
	N003	
	N003	
	N032	
	N033	
	N039	
	N040	
	N044	
	N049	
	N052	
	N055	
	N058	
	N059	
	N170	
	N171	
	N172	
	N178	
	N179	
	N189	
	N19	Exclude renal anemia, afunctional kidney, and alimentary proteinuria
Liver dysfunction	B150	
	B159	
	B162	
	B169	
	B171	
	B172	
	B178	
	B179	
	B181	
	B182	
	B189	
	B190	
	B199	
		20NEIDENTI AI

Variable Used in Study	ICD-10 Code*	Additional rules on Data Extraction
In Study	C220	
	K700	
	K701	
	K703	
	K709	
	K716	
	K720	
	K721	
	K729	
	K730	
	K732	
	K738	
	K739	
	K740	
	K741	
	K743	
	K744	
	K745	
	K746	
	K750	
	K751	
	K754	
	K759	
	K760	
	K761	
	K762	
	K763	
	K766	
	K767	
	K768	
	K769	
Cancer	C00	
	C01	
	C02	
	C03	
	C04	
	C05	

Variable Used in Study	ICD-10 Code*	Additional rules on Data Extraction
	C06	
	C07	
	C08	
	C09	
	C10	
	C11	
	C12	
	C13	
	C14	
	C15	
	C16	
	C17	
	C18	
	C19	
	C20	
	C21	
	C22	
	C23	
	C24	
	C25	
	C26	
	C30	
	C31	
	C32	
	C33	
	C34	
	C37	
	C38	
	C40	
	C41	
	C43	
	C44	
	C45	
	C46	
	C47	
	C48	

Variable Used in Study	ICD-10 Code*	Additional rules on Data Extraction
	C49	
	C50	
	C51	
	C52	
	C53	
	C54	
	C55	
	C56	
	C57	
	C58	
	C60	
	C61	
	C62	
	C63	
	C64	
	C65	
	C66	
	C67	
	C68	
	C69	
	C70	
	C71	
	C72	
	C73	
	C74	
	C75	
	C76	
	C78	
	C79	
	C80	
	C81	
	C82	
	C83	
	C84	
	C85	
	C88	

Variable Used in Study	ICD-10 Code*	Additional rules on Data Extraction
	C90	
	C91	
	C92	
	C93	
	C94	
	C95	
	C96	
	C97	
	D00	
	D01	
	D02	
	D03	
	D04	
	D05	
	D06	
	D07	
	D09	
	D10	
	D11	
	D12	
	D13	
	D14	
	D15	
	D16	
	D17	
	D18	
	D19	
	D20	
	D21	
	D22	
	D23	
	D24	
	D25	
	D27	
	D28	
	D29	

Variable Used in Study	ICD-10 Code*	Additional rules on Data Extraction
	D30	
	D31	
	D32	
	D33	
	D34	
	D35	
	D36	
	D37	
	D38	
	D39	
	D40	
	D41	
	D42	
	D43	
	D44	
	D45	
	D46	
	D48	

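### The SAP's peptic ulcer code list is over-inclusive, and its renal and alcohol lists are incomplete within N18 and F10

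*SAP*

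**What the plan says.** In the first analysis step of SAP 2.1, "patients with at least one predetermined high bleeding risks will be extracted". The 15 factors include "patients with renal dysfunction diagnosis", "patients with alcohol abuse" and "patients with a history of peptic ulcer diagnosis". The second step tests each of the 15 for interaction with treatment. The third repeats the weighted analysis in subgroups that are large enough.

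Peptic ulcer and renal impairment are on the candidate list in SAP 2.2.4, in the subgroup table in 4.4 and in the analysis summary in 7.2.3. Alcohol abuse is one of four factors with fewer than 2,000 patients at feasibility. Of these, SAP 2.2.4 says "Due to the insufficient statistical power, these subgroups could be eliminated from the further subgroup analysis", with the final decision left to a formal evaluation of subgroup size. Protocol section 8 is firmer and says they will not be analysed.

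Under SAP 5.4 each flag is set by at least one listed code in the baseline period. The lists are:

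- **Peptic ulcer (10.3.6):** F54 (restricted to psychogenic gastric ulcer), K221, K227 ("Include only Barrett's esophagus"), K25, K26, K27, K28, K51, K626, K633.
- **Renal impairment (10.3.1, to which 10.3.6 refers):** I120, I129, I139, eleven codes from N00 to N05, N170, N171, N172, N178, N179, N189, and N19 ("Exclude renal anemia, afunctional kidney, and alimentary proteinuria").
- **Alcohol abuse (10.3.6):** E244, E52, F100, G312, G405, G621, G701, G721, H470, I426, K292, K70, K852, K860, T519.

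The SAP gives no reason for these choices. Renal dysfunction is a propensity score covariate in SAP 7.1.1; peptic ulcer and alcohol abuse are not.

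**The concern.** A reader of the results will take each factor at its label. If the peptic ulcer flag admits other conditions, the subgroup estimate and the interaction test under that name describe a mixed group. If the renal or alcohol list leaves out codes that carry the stated condition, some patients who have it are counted as not having it. That blurs the comparison between patients with and without the factor.

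The renal case has a further consequence. Its flag is the means by which the propensity score adjusts for kidney disease, so an incomplete flag could leave part of that confounding in the primary comparison. All three flags also count towards cohort entry.

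**Working it through.** The plan states no figure on this point to reproduce. The check sets each list against its label.

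**1. Peptic ulcer.** There are 10 entries, and four are the blocks K25-K28. SAP 10.3.4 prints labels for members of K25, K26 and K28 as gastric, duodenal and gastrojejunal ulcer; in ICD-10, K27 is peptic ulcer of unspecified site. F54 is restricted to a gastric ulcer and fits the factor. The other five are:

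- K227: the SAP's own note makes it Barrett's esophagus, which is not a peptic ulcer.
- K51, K626 and K633: all outside K25-K28, with no restricting note. SAP 10.3.4 labels the neighbouring K625 as bleeding of the anus and rectum, which places K626 in an anorectal block. In ICD-10, K51 is ulcerative colitis and K633 is ulcer of the intestine; the SAP does not print either meaning.
- K221: SAP 10.3.4 labels K228 as oesophageal disease and K226 as gastro-oesophageal laceration with bleeding. Whether an oesophageal code belongs under this label is for the sponsor to state.

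Four of the 10 entries should therefore go, five stay and one needs a decision.

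**2. Renal.** The list has 21 distinct codes: 3 hypertensive renal + 11 from N00-N05 + 5 from N17 + 1 from N18 + 1 (N19) = 21. N17 is covered by five subcodes and N18 by N189 alone. In ICD-10, N189 is unspecified chronic kidney disease, and other N18 subcodes carry stage. A patient whose only renal code is one of those is flagged as having no renal dysfunction.

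**3. Alcohol.** The list has 15 codes: 1 from F10 and 14 others, mainly alcohol-related organ disease. K70 enters as a whole block, whereas F10 enters only through F100. In ICD-10, harmful use and dependence are other F10 subcodes. A patient coded only to those is missed.

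**4. Why the renal flag matters.** SAP 7.1.1 has no other direct renal covariate; eGFR and creatinine are defined in 5.4 but are not in the propensity model. The tables in SAP 7.1.9 give major bleeding rates (%/year) for moderate to severe renal dysfunction, which is not the same definition as the code flag:

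| Source | Warfarin, renal / overall | Apixaban/warfarin, renal | Apixaban/warfarin, overall |
|---|---|---|---|
| ARISTOTLE | 6.4/3.09 = 2.07 | 3.2/6.4 = 0.50 | 2.13/3.09 = 0.69 |
| CER3 | 3.32/2.81 = 1.18 | 2.21/3.32 = 0.67 | 1.69/2.81 = 0.60 |

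Both sources show more major bleeding on warfarin with renal dysfunction, so the covariate is worth measuring well. The rate ratios move in opposite directions, so the tables do not predict which way misclassification would shift a renal interaction.

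**5. Could the gap be caught later?** SAP 7.1.2 checks balance of baseline covariates after weighting, against a 10% standardized difference. SAP 7.1.6 adds unbalanced variables to the Cox model. An imbalance in eGFR or creatinine could enter that way where those values exist. Renal disease that the flag misses cannot appear as imbalance in the flag.

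**The case against.** The strongest reply is that the lists do contain their stated factors. The peptic ulcer list has all of K25-K28, the renal list has 20 codes besides N189, and the alcohol list has 14 besides F100. That stands. A reader might infer that the three flags fail to identify their factors; the contents show instead one list that is too wide and two with a gap.

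The second reply is that, apart from Barrett's esophagus, the argument uses ICD-10 meanings that the SAP does not print, and that nothing shows the omitted N18 and F10 subcodes are used in this database. This stands in part. ICD-10 is the coding system the SAP adopts, and the single entries under N18 and F10 are visible on the page. How often the omitted codes occur is unknown, and a patient with a staged code may also carry N189, N19 or a hypertensive renal code.

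Third, the SAP calls the subgroup analyses exploratory (3.2 and 7.1.7), and the balance check gives a second route for renal function. Both are true. Neither answers the labelling problem, and the balance check is only a partial safeguard because eGFR and creatinine are outside the propensity model.

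Fourth, a reader might infer that the alcohol subgroup fell below 2,000 because of missing codes. The documents do not say which list the feasibility count used, and SAP 2.2.4 already provides for a formal count before anything is dropped.

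**Conclusion.** The point holds for list content. The peptic ulcer list is over-inclusive by four of 10 entries, and this is the firmest part because the SAP's own note shows one of them. It affects a retained subgroup, an interaction test and a cohort-entry flag. The renal and alcohol lists are incomplete within N18 and F10. The renal gap matters more, since that flag is the only direct renal term in the propensity score.

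The size cannot be given. A reader might infer that the primary cohort is materially wrong, or want a percentage of misclassified patients. The documents support neither. Entry needs any one of 15 factors, including hypertension, diabetes, age over 80 and polypharmacy, so many affected patients may qualify anyway. No prevalence, per-factor count or share of patients coded only to omitted subcodes is reported.

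The conclusion assumes the standard ICD-10 meanings of K51, K633, N18 and F10, and that the code tables are complete as read. The start of the renal table is partly garbled, but the run N179, N189, N19 looks intact.

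**What to change.** - **Peptic ulcer (SAP 10.3.6):** remove K227, K51, K626 and K633. Keep K25-K28 and F54 with its gastric ulcer restriction. State whether K221 stays, and why.
- **Renal (SAP 10.3.1):** add the other N18 subcodes present in the database, keeping the hemodialysis exclusion in SAP 4.1.2. Use the revised flag in the propensity score as well as in the subgroup.
- **Alcohol (SAP 10.3.6):** add the F10 subcodes for harmful use and dependence.
- **Sequence:** apply the revised lists before the subgroup-size evaluation in SAP 2.2.4, so that decisions to keep or drop subgroups rest on them. Align Protocol section 8, which treats the alcohol subgroup as already dropped.

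The cost is a code-list edit and one recount in an existing database. The downside is a smaller peptic ulcer subgroup.
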